## Research Proposal

---

# Research Proposal

---

**2. Purpose:**

Low-level light/laser therapy (LLLT) has been proven effective in increasing cognitive function in several photobiomodulation models (Barrett and [name], 2013; Blanco et al., 2015). LLLT shows promise in its ability to minimize or prevent the loss of cognitive function associated with cardiovascular disease in high risk patients.

Cardiovascular diseases have been determined to be associated with diminished cognitive function. An ideal solution to this issue would be to restore proper cardiovascular status through improved lifestyles. However, an alternative intervention is increasing cerebral oxygen consumption by up-regulating mitochondrial respiration using LLLT. As shown by Haley et al., 2007, atherosclerosis of the carotid artery is a strong predictor of cognitive decline. The carotid artery intima media thickness (IMT) is also recognized as a risk factor for brain damage in asymptomatic patients (Nguyen-Thanh and Benzaquen, 2009).

We believe that the beneficial effects of LLLT can be used to combat the negative cognitive effects associated with vascular disease in high-risk patients. We hypothesize that, relative to their own baseline, participants who receive LLLT will exhibit improved cognitive performance (higher task accuracy, faster reaction times) in cognitive tests and have a greater Blood Oxygen Level Dependent (BOLD) fMRI response to a working memory task post-treatment. The therapeutic response to LLLT will likely be moderated by level of carotid atherosclerosis (measured by IMT) and genes involved in lipid transport (APOE).

**3. Procedures:***Summary of general design and methodology.*

We would classify this research study as a “non-significant risk device” study. Cognitive performance will be evaluated in working memory tasks in middle-aged and older adults across three groups: low intima media thickness (IMT) (1 STD below the mean), average IMT (mean), and high IMT (1 STD above the mean). Within each group there will be two possible interventions: the LLLT treatment or the placebo treatment. Cognitive tests will emphasize attention and executive functions, which are impaired in adults with cardiovascular risk factors (Cohen et al., 2009) and are enhanced by LLLT in young adults (Barrett and [name], 2013). Carotid atherosclerosis will be measured and documented via vascular ultrasound. BOLD-fMRI response to cognitive tasks will be measured pre- and post-treatment to determine physiological response to LLLT. 100 men and 100 post-menopausal women, aged 45 and older, will participate in this study after providing written informed consent, for 1 session of cardiovascular assessment, 1 session of cognitive testing and MRI scanning, followed by 6

## Research Proposal

---

weekly sessions of LLLT/placebo treatments, followed by post-treatment cognitive testing and MRI scanning.

### *Sequence of events:*

#### Telephone Screening

Visit 1: Baseline cardiovascular assessment: 1 hour (Vascular Aging Lab, Bellmont Hall)

Visit 2: Baseline cognitive testing/MRI visit: 2-2.5 hours (Clinical Neuroscience Lab, Seay building; UT Imaging Research Center, Norman Hackerman Building)

*The order of Visits 1 & 2 is interchangeable. The visit that comes first will include the informed consent procedure.*

Visits 3-8: Treatment visits: 1 hour (Human Laser Lab, Seay building)

Visit 9: Post-treatment cognitive testing/MRI visit: 2-2.5 hours (Clinical Neuroscience Lab, Seay building; UT Imaging Research Center, Norman Hackerman Building)

Visit 10: One month post-treatment discontinuation cognitive testing visit: 1 hour (Clinical Neuroscience Lab, Seay building)

In an effort to reduce study burden for participants with Mild Cognitive Impairment, the visit to Bellmont Hall will be removed. Participants will come to the Seay building for all visits. They will undergo a shortened cardiovascular assessment at the Clinical Neuroscience Lab during visit 1.

### *Sequence of events:*

#### Telephone Screening

Visit 1: Abbreviated baseline cardiovascular assessment/cognitive testing: 1-2 hours (Clinical Neuroscience Lab, Seay Building)

Visit 2: Baseline MRI visit: 2 hours (Clinical Neuroscience Lab, Seay building; UT Imaging Research Center, Norman Hackerman Building)

Visits 3-8: Treatment visits: 1 hour (Human Laser Lab, Seay building)

Visit 9: Post-treatment cognitive testing/MRI visit: 2-2.5 hours (Clinical Neuroscience Lab, Seay building; UT Imaging Research Center, Norman Hackerman Building)

Visit 10: One month post-treatment discontinuation cognitive testing visit: 1 hour (Clinical Neuroscience Lab, Seay building)

### Research Protocols:

Interested participants who are eligible after the telephone screening will receive a packet of information in the mail including the study consent forms, medical history questionnaires, and maps and parking information (please see attachments: Initial contact cover letter.doc; Consent form.doc; Mailing Packet.pdf). The questionnaires in the Mailing Packet include: Medical Screening Questionnaire, Food Diary, Edinburgh Handedness Questionnaire, Beck Depression Inventory, State Trait Anxiety Questionnaire, Cognitive Difficulties Scale, and 36-Item Short Form Survey Instrument (SF-36). Should they continue to express interest in the study, they will be scheduled for their first study visit (see details below) and instructed to bring the completed Mailing Packet to their first visit.

## Research Proposal

---

### *Cardiovascular assessment.*

This visit will take place at the UT Cardiovascular Aging Lab located Bellmont Hall under the supervision of [name] (co-I). The assessments included in this visit were also included in the approved protocol #2011-07-0025. This study will be covered under consolidated IBC eProtocol IBC-2015-00143, "Cardiometabolic risk and brain function" (see attached file: IBC eProtocol Number.docx). Participants with MCI will undergo an abbreviated version of the assessment in the Clinical Neuroscience Lab under the supervision of [name] (PI). The lab has biosafety Level II certification and operates under consolidated IBC eProtocol IBC-2015-00143. Participants will be instructed to fast and refrain from caffeine and chewing gum for at least eight hours prior to their visit. During the visit, participants will undergo the following assessments:

- 1) Resting blood pressure will be measured non-invasively using arm and ankle cuffs while participants rest in a supine position.
- 2) Participant's waist and hip circumferences will be measured with a tape measure.
- 3) Body weight and height will be measured with a beam balance scale for the purpose of calculating body mass index (BMI)
- 4). Body composition will be measured non-invasively by dual energy X-ray absorptiometry (DEXA) using Lunar DPX by General Electric Medical Systems. This procedure requires the subject to lie down approximately five minutes on a padded table while a small arm that emits energy to measure tissue density passes overhead. The DEXA assessments are performed by appropriately trained operators for research purposes only, and not for medical diagnostic purposes. The DEXA unit is operated in compliance with the Texas Administrative Code and the Texas Department of Health Services under the medical supervision of [name]., UT University Health Services physician, and radiation safety oversight of the UT Office of Environmental Health and Safety. This measure will be removed from the protocol for participants with MCI.
- 5) Arterial Stiffness will be measured non-invasively using ultrasound. This measure will be removed from the protocol for participants with MCI.
- 6) A blood sample will be drawn (~ 15 mL) through venipuncture by a trained phlebotomist to measure cholesterol, triglycerides, blood glucose, insulin levels. Additionally, proteins related to inflammation and arterial stiffness will be measured due to their importance to vascular health and cognition. This measure will be removed from the protocol for participants with MCI. Instead, they will undergo a finger prick.
- 7) A saliva sample will be obtained using an OMNIgene saliva collection kit (DNA Genotek, Ontario, Canada) to test for the presence of genetic polymorphisms with relevance to lipid transport and atherosclerosis (ApoE e4). Due to the preliminary nature of the investigation, no information about the person's genetic status will be released to the participant. Participants who have consented to this portion of the study will be instructed to spit into a small tube until approximately 1 mL of saliva is obtained. Saliva samples awaiting genetic analyses will be stored under participants' study number according to proper storage temperatures in a biosafety level 2 area (SEA 4.111B) until they are transferred to the UT Austin DNA Sequencing Facility (DSF) for analysis.

### *Cognitive testing/MRI visit.*

## Research Proposal

---

This visit will take place at the UT Department of Psychology and the UT Imaging Research Center in the Norman Hackerman Building. The assessments included in this visit were also included in the approved protocol #2011-07-0025. Upon arrival, participants will be screened for a second time on paper or electronically to ensure that they are eligible to safely participate in an MRI study (please see attachment: IRC MRI Screening Form.pdf).

Prior to being scanned, participants will complete questionnaires and a brief battery of neuropsychological paper-and-pencil tests assessing attention, memory, visual-spatial functioning, and language at the UT Department of Psychology (please see attachment: Cognitive test packet.pdf, which includes the Mini-Mental Status Examination, Dementia Rating Scale, Clinical Dementia Rating Scale, Wechsler Test of Adult Reading, California Verbal Learning Test, Brief Visuospatial Memory Test, Trail Making Test A & B, WAIS Digit Span, Controlled Oral Word Fluency Test, Stroop Test, California Verbal Learning Test alternate, and Boston Naming Test). The cognitive testing during the last visit will also include the 36-Item Short Form Survey Instrument (SF-36), which was included as part of the mailing packet. They may also practice the experimental tasks to be performed in the scanner on a laptop or desktop computer. Participants with MCI will complete cognitive testing on visit 1 and MRI scanning on visit 2 to reduce study burden. They will be offered a snack after the abbreviated cardiovascular assessment is completed on visit 1, before cognitive testing begins.

Neuroimaging will be conducted at the UT Imaging Research Center in the Norman Hackerman Building. Participants will be asked to change into medical scrubs and to store their personal items in a locker. Upon entering the magnet room, participants will be given earplugs to wear (specially chosen to limit the sound intensity produced by the MRI scanner). They will be instructed to lie supine on a table. Participants will place their head inside a standard head coil. In order to acquire MR images, it is necessary that the subject's head does not move appreciably; they will therefore be outfitted with pads and wraps. We will adjust the head stabilizers until both stability and participant comfort are attained. At this point, any cables connecting the coil array to the scanner will be inspected and adjusted to guarantee the absence of any loops or direct contact with the subject. The table will then be slid into the scanner so that the participant's head and upper body are inside the scanner tube.

Once in the scanner, participants will always be given a "squeeze ball" as a top-priority communication device. They will be instructed that squeezing the ball indicates that they wish to stop the scan and/or need immediate assistance. This sounds an alarm in the control room where the researchers sit while running the MRI scanner. The scanner will be stopped if the alarm sounds during a scan. Standard communication and instruction is performed via a built-in intercom system. Participants will also be given a response pad for use during the cognitive task.

A typical scan session will take approximately 40 minutes. We will begin by taking a few anatomical MR images of the participant's brain (6-10 minutes). We will then collect a series of functional MR images (12 minutes) while the subject views visual displays and performs the cognitive and control tasks. Acquisition of magnetic resonance spectroscopy (MRS) and resting state functional MR data will take an additional 20 minutes. Participants will not be required to do anything during those acquisitions. Participants will be encouraged to terminate the session if they become uncomfortable in any way.

*Treatment visits: Low-level light therapy.*

## Research Proposal

---

LLLT or placebo will be administered once a week for 6 weeks, following the same stimulation procedure as in our previously-approved IRB protocols (2011-05-0022, 2015-09-0018) and as reported in Barrett and [name] (2013). Administration of LLLT consists of applying light of a specific wavelength (1064 nanometers) using a laser diode, the HD laser (Cell Gen Therapeutics, LLC). This apparatus is FDA-cleared for temporary relief of muscle and joint pain, muscle spasm, stiffness associated with arthritis, improving circulation, and relaxation of muscle tissue. The HD laser has been evaluated and the standard operating procedure reviewed by the University of Texas at Austin Laser Safety Program for the purpose of occupational safety. The individuals who will operate the HD laser have completed the OH 304 Laser Safety class through UT's Environmental Health and Safety office. Both participants and experimenters wear protective eyewear, though the administrators of the LLLT are careful not to shine the light in or near the eyes.

The diameter of the circular surface receiving the LLLT is 4 centimeters. The laser power output used is 3.4 Watts. The irradiance (or power density) used, 250 milliwatts/centimeter, as well as the cumulative fluence (or energy density) used, 60 Joules / centimeter, are the same parameters that showed psychologically beneficial effects in Schiffer et al. (2009) and in Barrett and [name] (2013), and the same parameters approved in our previous approved IRB protocol (2011-05-0022). From ANSI Z136.1-2007, Table 7, the Maximum Permissible Exposure (MPE) to skin at the emission wavelength is 1.0 W/ cm^2. (The MPE standard for this wavelength is unchanged in Table 7b of the 2014 revision of the ANSI Z136.1 Safe Use of Lasers.) At the power level described, the energy emitted by the HD laser at this setting is one quarter of the skin MPE (0.250 W/cm^2), exposure to it is not deemed harmful to tissue, and it causes no detectable physical damage and negligible heat. In fact, similar settings are used clinically by Cell Gen Therapeutics for the treatment of disorders such as lower back pain, sciatica, and migraine headaches.

The LLLT treatment will occur in Seay 3.304, a lockable room in the [name] lab that has been approved by the University of Texas at Austin Laser Safety Program for housing of the HD laser apparatus. The experimenter will lock both himself and the participant inside the room, put a sign on the outer door indicating that the apparatus is in use, and make sure that protective eyewear (900 nm - 1000 nm: 5+, 1000 nm - 2400 nm: 7+; 2900 nm - 10600 nm: 7+) is worn by both individuals, following the approved standard operating procedure for the [name] lab's use of the apparatus. The laser's power output is automatically calibrated by an internal mechanism, every time a power level is set by the user; however, in addition to this calibration, the power density in mW/cm^2 (and thus the energy density dose in J/cm^2) will be confirmed independently using a Newport model 1916-C power meter attached to a Newport model 918D-SL photodiode detector, prior to the onset of treatment.

The laser will be directed at the right side of the forehead, targeting the middle frontal gyrus of the cerebral cortex, the area of the brain with the strongest relationship between carotid IMT and working memory activation in our prior study (Haley et al., 2007). The treatment duration is eight minutes. The control group will undergo the same procedure as the treatment group, but will receive brief (5-second) stimulation to the intended site on the forehead, followed by 55 seconds of no stimulation, for each 1-minute cycle. Only a fraction of the transmitted light will penetrate the skin, skull and dura to the brain, and the vascularity of the scalp efficiently removes heat and prevents any significant heat accumulation.

# Research Proposal

---

During the treatment visits, LLLT-related cognitive enhancement will be assessed using two tasks: the psychomotor vigilance task (PVT), a test of sustained attention; and the delayed match-to-sample memory task (DMS), a test of visual working memory. These executive/cognitive processes are mediated by the frontal cortical regions that the LLLT treatments target. These tasks are the same as those approved in our previously-approved IRB protocols (2011-05-0022, 2015-09-0018).

The first test will be a pre-treatment baseline evaluation. (This will be preceded by a brief 1-minute-long introduction to both tasks; this data will not be recorded.) Then, after the first treatment with LLLT or placebo, participants will repeat the PVT and DMS tasks. Participants will again repeat the PVT and DMS tasks after the sixth (final) treatment is completed. We have previously demonstrated an improvement in performance on both the PVT and DMS tasks after LLLT treatment (Barrett and [name], 2013).

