### 8. Compensation:

Participants will receive \$200 upon study completion. Should participants wish to discontinue the study early, they will be compensated \$17 per study visit for each completed visit. Subjects will be paid at the end of their last visit, with a check, and they must sign the receipt.

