**Statistical Plan:**

1. Primary outcome measure (PVT) will be analyzed using mixed ANOVA with 1 between-subjects factor (Treatment Group) and 1 within subjects factor (Time). Cognitively unimpaired (CU) and MCI groups will be analyzed separately. The contrast of interest will be Treatment Group by Time interaction. Alpha level of significance will be set at 0.05.
  - a. Secondary outcome measures (2Back performance, % Correct and Reaction Time) will be analyzed using mixed ANOVA with 1 between-subjects factor (Treatment Group) and 1 within subjects factor (Time). Cognitively unimpaired (CU) and MCI groups will be analyzed separately. The contrast of interest will be Treatment Group by Time interaction. Alpha level of significance will be set at 0.05.
  - b. Secondary outcome measures (2Back activation intensity within 8 *a priori* ROIs) will be analyzed using mixed ANOVA with 1 between-subjects factor (Treatment Group) and 1 within subjects factor (Time), only for participants who can perform the task to criterion (%Correct>50%). Cognitively unimpaired (CU) and MCI groups will be analyzed separately. The contrast of interest will be Treatment Group by Time interaction. Alpha level of significance will be set at 0.05 due to the exploratory nature of the analysis.
  - c. *A priori* ROIs were chosen based on prior literature. They are as follows:

ROI#	x	y	z	size (mm2)	designation
1	-33	4	56	2087	Left middle frontal gyrus
2	-5	19	44	1651	Left medial frontal/superior frontal gyrus
3	37	-63	53	683	Right superior parietal lobule
4	-49	-52	44	1333	Left inferior parietal lobule
5	-44	45	13	1139	Left middle frontal gyrus
6	33	48	15	955	Right superior frontal gyrus
7	32	5	55	553	Right middle frontal gyrus
8	47	14	3	335	Right inferior frontal gyrus

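### The last primary-outcome PVT is tied to completing the sixth treatment, and none is scheduled for participants who stop treatment early but would still be tested

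*Protocol*

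**What the plan says.** The SAP (Statistical Plan, item 1) makes the PVT the primary outcome and analyses it by mixed ANOVA with factors Treatment Group and Time. "The contrast of interest will be Treatment Group by Time interaction". It adds: "Cognitively unimpaired (CU) and MCI groups will be analyzed separately". It does not list the levels of Time, define an analysis population or give a rule for missing PVT values.

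The Protocol (section 3, treatment visits) places the PVT and DMS within the treatment visits, at three points:
- Before treatment: "The first test will be a pre-treatment baseline evaluation".
- After the first treatment.
- At the end of the course: "Participants will again repeat the PVT and DMS tasks after the sixth (final) treatment is completed".

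The schedule then lists "Visit 9: Post-treatment cognitive testing/MRI visit: 2-2.5 hours". The text on that visit describes a paper-and-pencil battery and the scan; it does not mention the PVT.

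On early exit, section 7 gives a general right to withdraw from the study. Section 8, a payment clause, says: "Should participants wish to discontinue the study early, they will be compensated" per completed visit. Neither document distinguishes stopping treatment from leaving the study.

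**The concern.** The last PVT is triggered by completing treatment, which happens after randomisation. Followed as written, a participant who stops after the third session is never due an end-of-treatment PVT, even if willing to be tested.

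If the reasons for stopping relate to outcome differently in the two arms, those who have the last PVT are no longer comparable by randomisation. An analysis that needs that value would then compare selected participants. This is more than missing detail in the analysis plan, because a value that was never collected can only be modelled later.

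**Working it through.** **Tracing the text.**
1. The PVT is assessed during the treatment visits (Protocol section 3). That wording is the main evidence that Visits 9 and 10 would not supply it. Its absence from the Visit 9 battery is weak support, because that list covers paper-and-pencil tests and the PVT is a computer task (section 5).
2. Someone who stops after at least one session has the baseline and post-session-1 PVT and lacks only the last value.
3. A conventional repeated-measures ANOVA drops anyone missing a level of Time. A completers' comparison therefore follows if Time includes the last PVT and incomplete cases are dropped. The SAP states neither.

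**Inputs for size.** The documents give a target of 200 participants (section 6a) and "Alpha level of significance will be set at 0.05". They give no withdrawal rate, SD, allocation ratio or CU and MCI numbers, and they do not say whether tests are two-sided. There is no power calculation to reproduce. The assumptions are two-sided testing, 1:1 allocation, a normal approximation, SD of PVT change equal to 1, and 50 per arm within a stratum (200 / 2 strata / 2 arms, if the strata are equal).

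**Case A: stopping related to outcome in one arm only.** A fraction p stops in each arm. In one arm, stoppers' change is d SD worse than completers'; in the other, stopping is unrelated to outcome. The affected arm's mean over everyone randomised is (completers' mean) - p x d, so:
- bias of the completers' contrast = p x d
- SE = sqrt(2 / (50 x (1 - p)))
- error = P(|Z + bias/SE| > 1.96) when the arms as randomised do not differ

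| p | d (SD) | Bias (SD) | SE | Bias/SE | Two-sided error |
|---|---|---|---|---|---|
| 10% | 0.3 | 0.030 | 0.211 | 0.142 | 5.2% |
| 15% | 0.5 | 0.075 | 0.217 | 0.346 | 6.4% |
| 20% | 0.5 | 0.100 | 0.224 | 0.447 | 7.3% |
| 30% | 0.8 | 0.240 | 0.239 | 1.004 | 17.1% |

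**Case B: stoppers g SD worse in both arms.** With stopping fractions pA and pB:
- bias = (pA - pB) x g
- SE = sqrt(1/(50 x (1 - pA)) + 1/(50 x (1 - pB)))

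Results at 50 per arm:
- 10% in both arms, g = 0.5: bias 0, error 5.0%.
- 15% against 5%, g = 0.5: bias 0.05 SD, error 5.6%.
- 20% against 5%, g = 1.0: bias 0.15 SD, error 10.8%.
- 30% against 10%, g = 1.0: bias 0.20 SD, error 14.4%.

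**What the fix can retrieve.** In Case A, suppose a fraction f of stoppers in each arm still attends and they are typical of stoppers. The remaining bias is p x d x (1 - f)(1 - p) / (1 - p + p x f). This is zero at f = 1 and the full p x d at f = 0. The documents give no basis for f.

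**Loss of numbers alone.** With 80% power, the detectable difference is (1.96 + 0.842) x sqrt(2/n per arm). It rises from 0.56 SD at 50 per arm to 0.67 SD at 35 per arm (30% lost). Absent selection, the cost is precision only.

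**The case against.** The wording about the sixth treatment may be ordinary timing language, and no passage says that early stoppers go untested. A reader might infer that leaving the study is the only early exit, that the primary result will be a completers' comparison, and that nothing can be done at analysis. The documents do not support these readings:
- Section 8 is about payment and is not a discontinuation policy. The Data and Safety Monitoring Plan is a separate attachment that was not available, although section 6d describes its contents as risks, adverse events and protections.
- The SAP names no Time levels and no complete-case rule.
- A likelihood-based model can use the two earlier PVTs, under missing-at-random.

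The size can also be challenged. Case A puts informative stopping in one arm only. The course is six weekly sessions of eight minutes, and the protocol expects little heating, so heavy or arm-specific stopping is not evident. Some stoppers will leave altogether, and no schedule retrieves them.

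Finally, the hypothesis in Protocol section 2 concerns participants who receive LLLT, so an effect-of-receipt question is defensible. That supports keeping a completers' analysis. It does not make self-selected completers comparable between arms.

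These objections limit the strength of the point. What remains is that the last value of the primary outcome has no scheduled occasion for a participant who stops treatment but stays willing to be tested.

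**Conclusion.** The point holds in conditional form. The last PVT depends on completing treatment, and the primary contrast may become a completers' comparison if Time includes that PVT and incomplete cases are dropped. Modelling the earlier PVTs would repair this only partly and under an assumption the data cannot test.

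The size is unknown. Under the Case A assumptions the error ranges from negligible (5.2%) through modest (6.4% to 7.3%) to serious (17%), the last needing 30% stopping with a 0.8 SD difference in one arm. With equal and equally informative stopping there is no inflation. A reader might take 17% as the expected harm; nothing in the documents supports that. The case for acting is that the gap concerns the primary outcome and is cheap to close.

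**What to change.** **Protocol section 3, treatment visits.** State that the PVT and DMS are taken after the sixth treatment or, for a participant who has stopped treatment but not left the study, within a stated window around the date the sixth treatment would have fallen. If Visit 9 is the only visit such a participant attends, take them there and record the date. Keeping the existing trigger for those still on treatment avoids testing someone before a rescheduled sixth session.

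**Protocol section 8, or a new short section.** State that stopping treatment is not leaving the study, and that these participants are invited to Visits 9 and 10 with the existing per-visit payment. This changes outcome collection only; it alters no treatment or stopping rule.

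**SAP item 1.** Name the levels of Time. Analyse all randomised participants in their assigned arm using all available PVT data, for example with a likelihood-based mixed model. Keep the completers' analysis as supportive.

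**Cost.** A short amendment and a few extra runs of two existing computer tasks. Visit 9 is only partly convenient: its cognitive testing is in the Seay building, in a different laboratory from the laser room, and its scan is in another building. For stoppers, the PVT falls some time after last exposure, so the estimate reflects assignment to LLLT rather than full receipt of it.
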